In order to summarize Karnofsky/Lansky performance status, physical exam, vital signs, ECG, and laboratory data collected over time (including unscheduled visits), the assessments will be time slotted. Time windows will be defined for descriptive summary by visit. The following general rule will be applied in creating the assessment windows: if more than one assessment is done within the same time window, the assessment performed closest to the target date will be used. If two or more assessments within a time window are equidistant from the target date or on the same date, then the maximum will be used. For growth and ECG analysis, if two assessments within a time window are equidistant from the target date then the mean will be used. For laboratory data, if two assessments within a time window are equidistant from the target date or on the same date or on the same date, then records from central laboratory should take precedence over local laboratory records. Data from all assessments (scheduled and unscheduled), including multiple assessments, will be listed.

 Table 2-1
 Time windows for Karnofsky/Lansky performance status/Urinalysis

Time Window	Planned Visit Timing	Time Window Definition
On treatment		
Baseline (Week 1 Day 1)	On or before Study Day 1ª	≤ Study Day 1
Week 5 Day 1	Study Day 29	Study Days 27 – 31
Week 8 Day 1	Study Day 50	Study Days 43 – 57

Time Window	Planned Visit Timing	Time Window Definition
Every 8 weeks thereafter		
Week y=8+8*k	Study Day (8+8*k-1)*7+1	Study Day
(with k = 1, 2,, 6)		(8+8*k-1)*7+1-7 to
		(8+8*k-1)*7+1+7
Every 16 weeks thereafter		
Week y=56+16*k	Study Day (56+16*k-1)*7+1	Study Day
(with k = 1, 2,)		(56+16*k-1)*7+1-7 to
		(56+16*k-1)*7+1+7
End of treatment (EoT)		
EoT	Within 30 days after last dose	Earliest data available on or after EoT date up to and including 30 days after EoT
Post treatment ^b		
Post treatment follow-up 1	Post treatment study day 16*7	Post treatment Study Days 16*7 - 14 to 16*7 + 14
Post treatment follow-up k (with k = 2, 3,)	Post treatment study day 16*k*7	Post treatment study days 16*k*7 - 14 to 16*k*7 + 14

^bPost treatment study day 1=end of treatment date + 1 day

Table 2-2 Time windows for physical exam/vital signs/hematology/chemistry

Time Window	Planned Visit Timing	Time Window Definition
On treatment		
Baseline (Week 1 Day 1)	On or before Study Day 1 ^a	≤ Study Day 1
Week 2 Day 1	Study Day 8	Study Days 6 – 10
Week 3 Day 1	Study Day 15	Study Days 13 – 17

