Week 4 Day 1	Study Day 22	Study Days 20 – 24
Week 5 Day 1	Study Day 29	Study Days 27 – 31
Week 8 Day 1	Study Day 50	Study Days 43 – 57
Every 8 weeks thereafter		
Week y=8+8*k	Study Day (8+8*k-1)*7+1	Study Day
(with k = 1, 2,, 6)		(8+8*k-1)*7+1-7 to
		(8+8*k-1)*7+1+7
Every 16 weeks thereafter		
Week y=56+16*k	Study Day (56+16*k-1)*7+1	Study Day
(with k = 1, 2, …)		(56+16*k-1)*7+1-7 to
		(56+16*k-1)*7+1+7
End of treatment (EoT)		
EoT	Within 30 days after last dose	Earliest data available on or

Time Window	Planned Visit Timing	Time Window Definition
		after EoT date up to and including 30 days after EoT
Post treatment ^b		
Post treatment follow-up 1	Post treatment study day 16*7	Post treatment Study Days 16*7 - 14 to 16*7 + 14
Post treatment follow-up k (with k = 2, 3,)	Post treatment study day 16*k*7 30	Post treatment study days 16*k*7 - 14 to 16*k*7 + 14

^aStudy Day 1 = start date of study treatment

^bPost treatment study day 1=end of treatment date + 1 day

Table 2-3 Time windows for ECG/Visual Acuity

Time Window	Planned Visit Timing	Time Window Definition
On treatment		
Baseline (Week 1 Day 1)	On or before Study Day 1 ^a	≤ Study Day 1
Week 5 Day 1	Study Day 29	Study Days 27 – 31
Week 16 Day 1	Study Day 106	Study Days 99 – 113
Week 32 Day 1	Study Day 218	Study Days 211 – 225
Week 48 Day 1	Study Day 330	Study Days 323 – 337
Week 72 Day 1	Study Day 498	Study Days 491 – 505
Every 16 weeks thereafter		
Week y=16+16*k	Study Day (16+16*k-1)*7+1	Study Day
(with k = 1, 2,)		(16+16*k-1)*7+1-7 to
		(16+16*k-1)*7+1+7
End of treatment (EoT)		
EoT	Within 30 days after last dose	Earliest data available on or
		after EoT date up to and
		including 30 days after EoT

For all analyses regarding abnormal assessments or analyses based on worst or best postbaseline value (laboratory, ECGs, vital signs, Karnofsky/Lansky performance status, echocardiogram (ECHO), ophthalmologic exam, dermatologic exam, etc.), all post-baseline values will be included (scheduled, unscheduled, repeat).

Last contact date

The last contact date will be derived for patients not known to have died at the analysis cut-off using the last complete date among the sources specified in Table 2-4.

Table 2-4	Last contact date	data sources
	Luot contact auto	

Source data	Conditions
Date of Randomization	No Condition
Last contact date/last date patient was known to be alive from Survival Follow-up page	Patient status is reported to be alive, lost to follow-up or unknown.

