For each ECG parameter, descriptive statistics at baseline, at each post-baseline time point and changes from baseline at each post-baseline time point will be summarized. Descriptive statistics at worst post-baseline and changes from baseline to worst post-baseline will also be summarized separately.

For each of the QTc and QT intervals, shift tables based on notable parameter categories (<450, 450-<481, 481-<501, ≥501 ms) at baseline and the worst post-baseline value observed.

Frequency counts and percentages of patients with newly occurring post-baseline qualitative ECG abnormalities (morphology) will be summarized. The denominator to calculate percentages is the number of patients with both a baseline and a post-baseline evaluation. A newly occurring post-baseline qualitative ECG abnormality is defined as a post-baseline abnormal finding which was not present at baseline.

Patients with notable ECG interval values and newly occurring qualitative ECG abnormalities will be listed and the corresponding notable values and abnormality findings will be included in the listings.

Unscheduled ECG measurements will not be used in computing the descriptive statistics for change from baseline at each post-baseline time point. However, they will be used in the analysis of notable ECG changes and the shift table analysis of notable QT parameters.

ECHO Data handling

ECHO data will be analyzed based on local reported results. The summaries will include all ECHO assessments performed no later than 30 days after the last date of study drug. All ECHO assessments will be listed, and those collected later than 30 days after study drug discontinuation will be flagged in the listing.

Novartis	Confidential	Page 37
SAP Final Analysis HGG		CDRB436G2201

The same modality (ECHO or MUGA) for determining cardiac scan data (e.g., left ventricular ejection fraction (LVEF)) should be used to follow a patient throughout the study. The absolute change from baseline values will not be calculated for any patients where the post-baseline value was determined by a cardiac scan modality that is different than the one used to determine baseline value.

ECHO Data analysis

Absolute change from baseline in LVEF will be summarized in the worst case post-baseline. Only the post-baseline assessments that used the same method (ECHO or MUGA) as the baseline assessments will be used to derive the change from baseline. The change from baseline will be categorized as follows:

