2.8.4.8 Ophthalmologic exam

Visual acuity will be converted from snellen to logMAR scale as defined in [Holladay 1997 (20)], and categorized as the following change from baseline:

- Improvement: $\geq 0.2 \log MAR$ improvement (decrease in logMAR)
- Stable: neither \geq 0.2 logMAR improvement nor worsening, where
- Worsening: $\geq 0.2 \log MAR$ worsening (increase in logMAR)

Visual acuity categories at each time point, as well as best and worst category on treatment will be presented.

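### Table 2-3 of both final SAPs contradicts itself after week 72: the ECG and visual-acuity window formula gives weeks 80, 96 and 112 where its own label and the SAP's visit grid give 88, 104 and 120

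*SAP*

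**What the plan says.** Section 2.1.1 of each final SAP assigns repeated assessments to visits by day windows. It states their purpose as "Time windows will be defined for descriptive summary by visit".

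Table 2-3 covers ECG and visual acuity. It lists baseline and weeks 5, 16, 32, 48 and 72 one by one; the week 72 row has target day 498 and window "Study Days 491 – 505". The next row is labelled "Every 16 weeks thereafter". It defines week 16+16k for k = 1, 2, and so on, with target "Study Day (16+16*k-1)*7+1" and a window of 7 days either side.

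Tables 2-1 and 2-2 (performance status and urinalysis; physical examination, vital signs and laboratory data) have 8-weekly visits to week 56. Their 16-weekly rows then use "Study Day (56+16*k-1)*7+1".

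Two outputs rely on Table 2-3:

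- **ECG (Section 2.8.4.1):** "descriptive statistics at baseline, at each post-baseline time point and changes from baseline at each post-baseline time point will be summarized". Unscheduled ECGs are barred from the by-visit change-from-baseline statistics.
- **Visual acuity (Section 2.8.4.8):** "Visual acuity categories at each time point, as well as best and worst category on treatment will be presented".

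For abnormal-value and worst- or best-value analyses, Section 2.1.1 says that "all post-baseline values will be included (scheduled, unscheduled, repeat").

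**The concern.** A continuation row placed after week 72 should start at week 88. This one starts at week 32, so label and formula cannot both be right. The formula also disagrees with the calendar in the two neighbouring tables, where week 72 is a visit and weeks 64, 80 and 96 are not.

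The windows are narrow and I found no rule that moves an out-of-window record to the nearest visit. A programmer who follows the row literally would leave later on-schedule assessments unassigned and print columns for weeks at which no visit is due. Section 2.4.1 has an exposure category of 112 weeks or more, so treatment well past week 72 is expected. At stake is the late part of the by-visit ECG and visual-acuity tables in the final report.

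**Working it through.** **Inputs.** All come from Section 2.1.1 of the final SAPs: the listed rows of Table 2-3, its formula 16+16k with ±7 days, and the formula 56+16k from Tables 2-1 and 2-2. The day for a week is (week − 1) × 7 + 1.

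**Reproducing the listed rows.** Week 16: 15×7+1 = 106. Week 32: 31×7+1 = 218. Week 48: 47×7+1 = 330. Week 72: 71×7+1 = 498. With ±7 days the windows are 99–113, 211–225, 323–337 and 491–505. All agree with Table 2-3.

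**What the formula 16+16k generates.**

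| k | Week | Target day | Window | Remark |
|---|---|---|---|---|
| 1 | 32 | 218 | 211–225 | repeats a listed row |
| 2 | 48 | 330 | 323–337 | repeats a listed row |
| 3 | 64 | 442 | 435–449 | before week 72, not a visit in Tables 2-1 and 2-2 |
| 4 | 80 | 554 | 547–561 | not a visit in Tables 2-1 and 2-2 |
| 5 | 96 | 666 | 659–673 | not a visit in Tables 2-1 and 2-2 |
| 6 | 112 | 778 | 771–785 | not a visit in Tables 2-1 and 2-2 |
| 7 | 128 | 890 | 883–897 | not a visit in Tables 2-1 and 2-2 |

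**What 16-weekly visits after week 72 give.** 72+16k is 88, 104, 120, and so on. The formula 56+16k gives 72, 88, 104, 120, which is the same series from its second term.

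| Week | Day | Day ±7 | Nearest windows as written | Days to nearest edge |
|---|---|---|---|---|
| 88 | 610 | 603–617 | 547–561 and 659–673 | 610 − 561 = 659 − 610 = 49 |
| 104 | 722 | 715–729 | 659–673 and 771–785 | 722 − 673 = 771 − 722 = 49 |
| 120 | 834 | 827–841 | 771–785 and 883–897 | 834 − 785 = 883 − 834 = 49 |

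A visit 7 days off target still touches no window. The offset does not close later: both series step by 16 weeks and stay 8 weeks (56 days) apart, which less the 7-day half-width is 49 days. Enumeration to week 248 found no match.

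**What the off-grid windows would hold.** For the by-visit ECG change-from-baseline statistics, the week 80, 96 and 112 windows would be essentially empty, because unscheduled ECGs are excluded from that output. For visual acuity I found no such exclusion, so those columns could hold a few off-schedule records.

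**Where else the formula stands.** The row is the same in both final SAPs and in both SAPs dated 30-Sep-2021.

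**The case against.** The strongest reply is that week 72 may be the slip. Weeks 16, 32 and 48 followed by 64, 80 and 96 form an unbroken 16-weekly series. The protocol schedule is not at hand, and weeks 88, 104 and 120 are nowhere printed for ECG or visual acuity. This stands as a caution: if the protocol uses 64, 80 and 96, a change to 72+16k would create the loss it is meant to cure. It does not rescue the table, because week 72 would then not belong and the continuation would still restart at week 32. The SAPs' own calendar also favours week 72, which is on the 56+16k grid while 64, 80 and 96 are not.

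The second reply is that the effect is narrow. That is correct. Notable-value, shift and worst/best analyses use all post-baseline values, every assessment is listed, and the end-of-treatment assessment has its own window. No inference or efficacy result depends on these windows.

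A reader might infer more than the documents support:

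- **That all late ECG and visual-acuity assessments are certainly lost.** This depends on the inferred visit calendar.
- **That the planned 2 years of follow-up means each patient loses at least two visits.** The 2 years refer to survival follow-up, not time on treatment.
- **That late vision data disappear for LGG patients enrolled with impaired vision.** Section 2.8.4.8 of the LGG final SAP plans a separate logMAR plot for these patients and states no window restriction for it.

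**Conclusion.** The point holds as an internal contradiction in Table 2-3 of both final SAPs; that much needs no assumption. The size of the loss is conditional. If ECG and visual-acuity visits after week 72 follow the 56+16k grid, every on-schedule assessment after week 72, other than one captured by the end-of-treatment window, falls outside all windows. It is then missing from the by-visit ECG descriptive and change-from-baseline statistics and from the by-visit visual-acuity categories. A patient with on-schedule assessments at weeks 88 and 104 would lose both from those tables. The number of patients concerned cannot be given, because the SAPs do not report how many were treated past week 72. The consequence is confined to descriptive safety tables, but the rule is wrong as written and should be corrected.

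**What to change.** Check the ECG and visual-acuity schedule in the protocol and reconcile the last repeating on-treatment row of Table 2-3 with it, in both final SAPs. On the SAPs' own calendar the row becomes week 72+16k (k = 1, 2, and so on), target day (72+16k−1)×7+1, ±7 days. That gives week 88 = day 610 (603–617), week 104 = day 722 (715–729), week 120 = day 834 (827–841) and week 136 = day 946 (939–953). If the protocol instead schedules weeks 64, 80 and 96, the week 72 row should be corrected and the formula started after week 48.

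This changes an analysis window only, not a clinical visit. The cost is one row per SAP, the matching programming specification, and a rerun of the by-visit ECG and visual-acuity tables. Since the 2021 SAPs carry the same row, check whether the by-visit tables produced under them have the same gap before setting old and new tables side by side.

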2.2 Analysis sets

Full Analysis Set

The **Full Analysis Set** (FAS) comprises all patients to whom study treatment has been assigned and who received at least one dose of study treatment.

Safety Set

The **Safety Set** includes all patients who received at least one dose of any component of the study treatment.

Evaluable Set

The **Evaluable Set** consists of all evaluable patients in the FAS who have:

- centrally confirmed HGG through histology, and
- centrally confirmed positive BRAF V600 mutation, and
- an adequate tumor assessment at baseline, (An adequate tumor assessment at baseline refers to baseline measurable disease assessed by investigator and confirmed by central independent reviewer per RANO criteria), and

Novartis	Confidential	Page 16
SAP Final Analysis HGG		CDRB436G2201

• either 1) a follow-up tumor assessment at week 8 day 1 visit or later (any assessment on or after day 43 allowing for the time-window around the visit) or 2) disease progression at any time or 3) have discontinued for any reason.

The evaluable set will be used for sensitivity analyses as defined in Section 2.5 and Section 2.7.

Patient Classification:

Patients may be excluded from the analysis populations defined above based on specific patient classification rules defined in Table 2-5 Patient classification rules for analysis sets Reasons leading to exclusion from analysis sets will be listed.

Analysis set	Criteria leading to exclusion
FAS	No dose of study medication
Safety Set	No dose of study medication
Evaluable Set	Not centrally confirmed measurable disease at baseline,
	Not centrally confirmed HGG,
	Not centrally confirmed BRAF V600 mutant,
	Patients who do not have an adequate tumor assessment at baseline
	Patients who do not have a follow-up tumor assessment at least 43 days after starting treatment unless disease progression is observed before that time or patient discontinued for any reason.

Table 2-5Patient classification rules for analysis sets

Withdrawal of Informed Consent

Any data collected in the clinical database after a patient withdraws informed consent from all further participation in the trial, will not be included in the analysis data sets. The date on which a patient withdraws full consent is recorded in the eCRF.

Death events may be used in the analysis if captured from public records (registers), local law and subject informed consent permitting.

Additional data for which there is a separate informed consentcollected in the clinical database without having obtained that consent will not be included in the analysis. These data will be excluded by the presence of the appropriate protocol deviation criterion.

2.2.1 Subgroups of interest

Efficacy

No subgroup analyses of efficacy data are planned for the final CSR.

Safety

Safety subgroup analyses will use the same method as for the analysis in the safety analysis set. Key safety analyses including:

- Overview of AEs
- AEs, regardless of relationship to study drug, by primary system organ class (SOC) and preferred term (PT)
- AEs related to the study drug, by primary SOC and PT
- Serious AEs, regardless of relationship to study drug, by primary SOC and PT

will be repeated on safety set in the following subgroups:

- Age group at enrollment (12 months- <6 years, 6 -< 12 years, 12 -< 18 years)
- Any prior antineoplastic chemotherapy (yes, no)

The objective for carrying out these subgroup analyses is to identify potential safety issues that may be limited to a subgroup of patients, or safety issues that are more commonly observed in a subgroup of patients.

2.3 Patient disposition, demographics and other baseline characteristics

The FAS will be used for all baseline and demographic summaries and listings unless otherwise specified.

For the final database lock, no analyses will be performed on basic demographic and background data, diagnosis and extent of cancer, medical history or other baseline data. As there have been no changes to patient enrollment since the primary analysis, the analyses performed for the primary analysis can be referred to for all baseline data.

2.3.1 Patient disposition

The number (%) of patients in the FAS who completed treatment, who discontinued the study phases and the reason for discontinuation will be presented.

The following summaries will be provided: % based on the total number of FAS patients:

- Number (%) of patients who were treated (based on 'DAR' eCRF pages of each study treatment component completed with non-zero dose administered);
- Number (%) of patients who completed the study treatment phase (based on the 'End of Treatment Disposition' page)
- Number (%) of patients who discontinued the study treatment phase (based on the 'End of Treatment Disposition' page)
- Primary reason for study treatment phase discontinuation (based on the 'End of Treatment Disposition' page)
- Number (%) of patients who have entered the post-treatment follow-up (based on the 'End of Treatment Disposition' page);

- Number (%) of patients who have discontinued from the post-treatment follow-up (based on the 'End of Post Treatment Phase Disposition' page);
- Reasons for discontinuation from the post-treatment follow-up (based on 'End of Post Treatment Phase Disposition' page);
- Number (%) of patients who have entered the survival follow-up (based on the 'End of Treatment Disposition' or 'End of Post Treatment Phase Disposition' page).
- Number (%) of patients who have rolled over to long-term follow-up study G2401. (based on the 'EOT_Rollover' disposition page).

Protocol deviations

The number (%) of patients in the FAS with any protocol deviation will be tabulated by deviation category (as specified in the study Data Handling Plan). All protocol deviations will be listed.

2.4 Treatments (study treatment, rescue medication, concomitant therapies, compliance)

2.4.1 Study treatment / compliance

Duration of exposure, actual cumulative dose, dose intensity (DI) and relative dose intensity (RDI) will be summarized separately for dabrafenib and trametinib. The duration of exposure will also be presented for the study treatment of dabrafenib and trametinib combination therapy. Duration of exposure will be categorized into time intervals; frequency counts and percentages will be presented for the number (%) of patients in each interval. The number (%) of patients who have dose reductions or interruptions, and the reasons, will be summarized by dabrafenib and trametinib. The number (%) of patients with a dose re-escalation will also be summarized by treatment group.

Patient level listings of all doses administered on treatment along with dose change reasons will be produced.

The safety set will be used for all summaries and listings of study treatment.

Duration of exposure to study treatment

Duration of exposure to study treatment is considered by taking into account the duration of exposure to any combination partner.

Duration of exposure to study treatment (days) = (last date of exposure to study treatment) - (date of first administration of study treatment) + 1.

The last date of exposure to study treatment is the latest of the last dates of exposure to any combination partner (see Table 2-6 Definition of last date of exposure of study drug).

Summary of duration of exposure of study treatment in appropriate time units based on clinically meaningful time intervals (eg 8-<24, 24-<56, 56-<112, >= 112 (weeks)) will include categorical summaries and continuous summaries (i.e. n, mean, standard deviation, median, 25^{th} - 75^{th} percentiles, minimum, and maximum) using appropriate units of time.

Duration of exposure to combination partner

Duration of exposure to a study drug (days) = (last date of exposure to investigational drug) -(date of first administration of investigational drug) + 1.

Page 19

Table 2-6 Definition of last date of exposure of study drug

Definition of last date of exposure of study drug	Example
Date of last administration of a non -zero dose of the study drug.	A patient had a permanent discontinuation of the study drug 06Jan2013 after being put on a temporary interruption since 01Jan2013. In this case the last date of exposure is 31Dec2012.

Summary of duration of exposure to each combination partner will include categorical summaries based on clinically meaningful time intervals (8-<24, 24-<56, 56-<112, >= 112 (weeks)) and using descriptive statistics (i.e. n. mean, standard deviation, median, 25th-75th percentiles, minimum, and maximum) using appropriate units of time.

Cumulative dose and average daily dose

Cumulative dose of a study treatment is defined as the total dose given during the study treatment exposure and will be summarized for each of the study drug, respectively. Average daily dose is defined as [Cumulative dose (dosing unit) / Number of dosing days]; drug free days are not counted as dosing days.

Cumulative dose and average daily dose will be summarized both in mg and mg/kg. Total actual cumulative dose (mg/kg) of dabrafenib and trametinib is calculated as the sum of the daily doses in mg/kg, where the mg/kg dose on any particular day is calculated as the dose in mg divided by the current weight (collected as per the visit schedule). Total actual cumulative dose (mg) of dabrafenib and trametinib is calculated as the sum of the daily doses in mg.

The **planned cumulative dose** for a study treatment component refers to the total planned dose as per the protocol up to the last date of study drug administration. The planned dose (mg) will be taken from the planned dose (mg) times the frequency from the first dosing record. The planned cumulative dose will not be summarized/listed. It will be used for relative dose intensity calculations.

The **actual cumulative dose** refers to the total actual dose administered over the duration for which the patient is on the study treatment as documented in the DAR eCRF page.

For patients who did not take any drug, the actual cumulative dose is by definition equal to zero for that drug.

For continuous dosing, the actual cumulative dose is the sum of the non-zero doses recorded over the dosing period and the planned cumulative dose is the planned starting dose summed over the same dosing period.

Dose intensity and relative dose intensity

Dose of dabrafenib and trametinib will be defined in the units of mg, and taken from the DAR eCRF.

Dose intensity (DI) for patients with non-zero duration of exposure is defined as follows:

DI (mg/day) = Actual Cumulative dose (mg) / Duration of exposure (day).

For patients who did not take any drug the DI is by definition equal to zero.

Planned dose intensity (PDI) is defined as follows:

PDI (mg/ day) = Planned Cumulative dose (mg) / Duration of exposure (day).

Relative dose intensity (RDI) is defined as follows:

RDI = DI (mg/day) / PDI (mg/day).

DI and RDI will be summarized separately for each of the study treatment components, using the duration of exposure of each of the components.

Summary of RDI will include categorical summaries based on clinically meaningful intervals ($\leq 50\%$, $>50-\leq 75\%$, $>75-\leq 90\%$, $>90-\leq 110\%$, >110%).

 Table 2-7
 Examples of dabrafenib dose administration and exposure

DAR record number	Start/End Date	Dose Prescribed (mg) frequency	Dose Administere d (mg) [total daily]	Dose Changes, Dose Interruption ?	Dose Permanently Discontinued	Reason
1	01Jan2016 / 05Jan2016	125 mg BID	250	No	No	
2	06Jan2016 / 03Feb2016	125 mg BID	200	Yes	No	AE
3	04Feb2016 / 25Feb2016	130 mg BID	260	Yes	No	As per protocol

Duration of exposure (days) = 25Feb2016 - 01Jan2016 + 1 = 56 days

Planned cumulative dose (for 56 days) = 125*2*56 days = 14000 mg

Actual cumulative dose = 250*5 + 200*29 + 260*22 = 12770 mg

Dose intensity = 12770 mg / 56 days = 228.04 mg/day

Planned dose intensity = 14000 mg / 56 days = 250 mg/day

Relative dose intensity = DI / PDI = (228.04 mg/day) / (250 mg/day) = 91.2%

Table 2-8	Examples of trametinib dose administration and exposure
-----------	---

DAR record number	Start/End Date	Dose Prescribed (mg), frequency	Dose Administere d (mg) [total daily]	Dose Changes, Dose Interruption?	Dose Permanently Discontinued	Reason
1	01Jan2016 / 10Jan2016	0.875 QD	0.875	No	No	
2	11Jan2016 / 15Jan2016	0.875 QD	0	Yes	No	AE

DAR record number	Start/End Date	Dose Prescribed (mg), frequency	Dose Administere d (mg) [total daily]	Dose Changes, Dose Interruption?	Dose Permanently Discontinued	Reason
3	16Jan2016 / 25Feb2016	0.75 QD	0.75	No	No	AE

Duration of exposure = 25Feb2016 - 01Jan2016 + 1 = 56 days

Planned cumulative dose (for 56 days) = 0.875*56 days = 49 mg

Actual cumulative dose = 0.875*10 + 0*5 + 0.75*41 = 39.5 mg

Dose intensity = 39.5 mg / 56 days = 0.705 mg/day

Planned dose intensity = 49 mg / 56 days = 0.875 mg/day

Relative dose intensity = DI / PDI = (0.705 mg/day) / (0.875 mg/day) = 80.6%

Dose reductions, interruptions, re-escalations or permanent discontinuations

The number of patients who have dose reductions, permanent discontinuations or interruptions, and the reasons, will be summarized separately for each of the study drug. The number of patients who have dose re-escalations will also be summarized.

'Dose interrupted' and 'Dose permanently discontinued' fields from the Dosage Administration eCRF pages will be used to determine the dose interruptions and permanent discontinuations, respectively. Dose reductions will be derived programmatically using the dosing information as described below.

The corresponding fields 'Reason for dose change/dose interrupted' and 'Reason for permanent discontinuation' will be used to summarize the reasons.

A dose change is either 'change in prescribed dose level' or 'dosing error' where actual dose administered/total daily dose is different from the prescribed dose.

For the purpose of summarizing interruptions and reasons, in case multiple entries for interruption that are entered on consecutive days with different reasons will be counted as separate interruptions. However, if the reason is the same in this block of entries, then it will be counted as one interruption.

Dose Reduction: Only dose change is collected in the eCRF, the number of reductions will therefore be derived programmatically based on the change and the direction of the change. A dose reduction is a dose change where the prescribed dose level is lower than the previous prescribed dose level or where the actual dose administered/total daily dose is lower than the calculated dose amount based on the prescribed dose. Note that any dose change due to dispensing or dosing error will not be considered a dose reduction. Note also that any previous dose interruptions and any previous dosing or dispensing errors should be ignored when considering whether a subsequent dose change counts as a dose reduction, i.e., if the new dose is lower than the dose prior to any dose interruption or any dose or dispensing error this would still constitute a dose reduction. Missing data: If dose is recorded but regimen is missing or entered as 'none', it is assumed that the investigational drug was taken as per-protocol.

Dose Re-escalation: For patients with a dose reduction, a dose re-escalation is where the prescribed dose level is higher than the previous prescribed dose level or where the actual dose administered/total daily dose is higher than the calculated dose amount based on the prescribed dose. An increase will only be considered a dose re-escalation if the reason for dose change is "as per protocol". Note also that any previous dose interruptions and any previous dosing or dispensing errors should be ignored when considering whether a subsequent dose change counts as a dose re-escalation.

